#### **3.2 Study Endpoints**

#### 3.2.1 Primary efficacy endpoint

The primary efficacy objective of the study is to evaluate the effect of Opaganib on total supplemental oxygen requirement (area under the curve) using daily oxygen flow (L/min) measurements for 14 days (Day 1 to Day 14).

The primary efficacy endpoint will calculate for each patient the area under the curve of the supplemental oxygen requirement through day 14, using the trapezoidal rule after subtracting the baseline oxygen requirement at each day.

The following rules will be applied:

- If several values of oxygen requirement (L/min) are recorded in a certain day, then for the primary analysis the highest of these values will be taken.
- Days where no supplementary oxygen was needed, will be recorded as 0.
- Subjects who require intubation and mechanical ventilation, at these days will be assigned the maximal supplemental oxygen flow requirement of 8L/min (or if higher, the maximal value observed in the study).
- For subjects discharged from hospital without requiring supplemental oxygen prior to Day 14, the oxygen requirement (L/min) will be assigned thereafter as 0 for each day to Day 14 (in the rare case that subject will re-hospitalize before Day 14, the new supplemental oxygen data will be collected and used, until day 14).
- For the primary analysis, if a patient dies any time before Day 14), all his/her values (D1-D14) will be assigned at the maximal supplemental oxygen flow requirement of 8L/min, or if higher, the maximal value observed in the study.

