# 5.2 Specification of Baseline Values

In general, Baseline will be defined for each subject as the last available, valid, nonmissing assessment before first study drug dose.

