### 7.2 Primary Efficacy Endpoint Analysis

The primary analysis will be based on the modified Intent to treat population (mITT), which consist of all patients that were randomized and treated with at least one dose of study drug,

The primary analysis will be based on the baseline-adjusted AUC calculated individually for each subject, as defined in section 3.2.1. Descriptive statistics of the baseline-adjusted AUC will be presented by group and group means will be presented along with 95% confidence interval. The difference in means between the groups will be estimated and presented with 95% confidence interval. Plots presenting individual baseline-adjusted AUC will be presented. Difference between group medians with confidence interval will also be estimated using the Hodges-Lehmann statistics and will be presented along with the non-parametric Wilcoxon rank sum test.

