#### 7.2.1.1 Missing data

The primary analysis above is based on individual AUC calculation, where in case that all supplemental oxygen values are missing after discharge or early treatment discontinuation that occur while subject still requires supplemental oxygen (before day 14), the last value is carried forward - until Day 14, or death, if occurred before. In addition, worst case imputation is applied for subjects who died any time within 14 days and on days of intubation.

A sensitivity analysis to the above missing data handling approach will be performed using an AUC summary statistics approach, in which groups AUC is calculated from the estimated parameters of a Repeated-Measures model. More specifically, taking as the dependent variable the observed daily oxygen requirement per each subject (change from baseline), a model incorporating factors for group, day (categorical) and group by day interaction will allow estimation of the mean oxygen requirement at each day, for each group. The model will be implemented using the MIXED procedure in SAS software with subject taken as random factor. To confirm that correlation among observations from the same subject are adequately modeled in this MIXED model application, the following correlation structures will be fitted as well: Unspecified (UN) and Autoregressive(1)

Statistical Analysis Plan	RedHill Biopharma
Version: 3, Date: 13-DEC-2020	Study ABC-110

(AR(1)). The denominator degrees of freedom will be computed using the Kenward-Roger method. Each group mean AUC will be estimated using a linear combination of the parameter estimates after a model has been fit. Group AUCs and their difference will be presented along with 95% confidence interval.

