#### 7.2.1.2 Baseline characteristics adjustment

Estimation of difference between the treatment groups when controlling for the stratification factors and baseline oxygen requirement will be performed, using regression analysis, both for the individual subjects AUC (via Analysis of Covariance) and the group AUC modeling via Repeated measures approach sensitivity analysis.

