#### 7.2.1.4 Robustness for outliers

Analysis based on ranked observations will be performed to confirm robustness of the estimated effect for potential outliers.

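### SAP 7.2: in the planned Wilcoxon test a death at high baseline oxygen can rank better than survival from a lower baseline, because each death scores 13 x (M - own baseline) (minor)

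*SAP*

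**What the plan says.** SAP 3.2.1 builds the primary score for each patient as an area under the daily oxygen flow from Day 1 to Day 14, "using the trapezoidal rule after subtracting the baseline oxygen requirement at each day". SAP 5.2 fixes the reference value: "Baseline will be defined for each subject as the last available, valid, nonmissing assessment before first study drug dose".

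Two rules in 3.2.1 assign a maximal flow, 8 L/min or the study maximum if higher (M below):

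- **Death before Day 14:** "all his/her values (D1-D14) will be assigned at the maximal supplemental oxygen flow requirement of 8L/min".
- **Ventilation:** "Subjects who require intubation and mechanical ventilation, at these days will be assigned the maximal supplemental oxygen flow requirement of 8L/min".

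The death rule replaces the Day 1 to Day 14 values. It does not replace the pre-dose baseline. SAP 7.2.1.1 summarises the two rules by saying that "worst case imputation is applied for subjects who died any time within 14 days and on days of intubation".

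SAP 7.2 presents group means and their difference first. It then adds a Hodges-Lehmann estimate on the same individual scores, which "will be presented along with the non-parametric Wilcoxon rank sum test". No separate rank is given to deaths. SAP 7.2.1.2 plans an adjusted estimate, "when controlling for the stratification factors and baseline oxygen requirement will be performed", by ANCOVA on the individual AUC and in the repeated-measures model. SAP 7.2.1.4 adds: "Analysis based on ranked observations will be performed to confirm robustness of the estimated effect for potential outliers".

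**The concern.** Calling the rule worst case suggests that a patient who dies carries the least favourable result in every analysis of the primary endpoint. Because each patient's own baseline is subtracted after the imputation, the score for a death shrinks as baseline oxygen rises. The trial enrols patients on regular oxygen as well as patients on positive pressure or high-flow cannula (SAP 3.4, 5.6), so baselines will differ widely. The Wilcoxon test orders all patients on this one score without a baseline covariate. A death from a high baseline can then count as a better result than survival on a ventilator from a lower baseline. If deaths differ between arms, the test would register less of that difference than a reader would expect.

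A related point does not depend on deaths. The unadjusted mean difference carries any chance imbalance in baseline flow. Minimisation uses a yes/no factor for type of support, not flow in L/min, so it restrains this imbalance without removing it.

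**Working it through.** The plan states no power or expected AUC to reproduce (SAP 3.3). The check is the arithmetic of the score.

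**Inputs.** Days 1 to 14 give 14 points and 13 unit intervals. M is at least 8 (SAP 3.2.1). The highest flow observed is not in the documents, so M = 8, 15, 40 and 60 are assumed as a range. A higher score is worse.

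**Scores.**

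- Death with baseline b: every daily change is M - b, so the score is 13 x (M - b).
- Survivor steady at baseline s, then ventilated from Day k (k at least 2) through Day 14: there are 14 - k full intervals and one half interval, so the score is (14.5 - k) x (M - s).

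**Equal baselines.** For k at least 2 the survivor's multiplier is at most 12.5, below 13. No daily value can exceed M, so death is worst or tied worst.

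**Different baselines.** Death ranks better when 13 x (M - b) < (14.5 - k) x (M - s), that is when b > M - (14.5 - k) x (M - s)/13. For s = 4:

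| M | Score, ventilated from Day 8 | Death ranks better if b > | Score, ventilated from Day 3 | Death ranks better if b > |
|---|---|---|---|---|
| 8 | 6.5 x 4 = 26 | 6 | 11.5 x 4 = 46 | 4.46 |
| 15 | 6.5 x 11 = 71.5 | 9.5 | 11.5 x 11 = 126.5 | 5.27 |
| 40 | 6.5 x 36 = 234 | 22 | 11.5 x 36 = 414 | 8.15 |
| 60 | 6.5 x 56 = 364 | 32 | 11.5 x 56 = 644 | 10.46 |

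Ventilation is not needed for a reversal. At M = 8, a survivor who rises from 2 to 5 L/min from Day 3 scores 1.5 + 11 x 3 = 34.5. That is worse than a death with b = 6, which scores 13 x 2 = 26. A death with b = M scores 0, level with a survivor whose oxygen need never changed.

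**Within the SAP 7.5 subgroups** (assumed M = 60, low-flow baselines 1 to 15, high-flow 20 to 60):

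- Every low-flow death scores at least 13 x 45 = 585. That is above the 364 of a survivor with baseline 4 ventilated from Day 8, but below the 644 of one ventilated from Day 3.
- A high-flow death with b = 45 scores 13 x 15 = 195. A high-flow survivor with baseline 20 ventilated from Day 8 scores 6.5 x 40 = 260.

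Subgrouping narrows the problem but does not remove it.

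**How much it matters.** The documents give no flow or mortality data, so this part is illustrative only. The assumptions are:

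- 2000 trials of 20 per arm, with 30% of patients on high flow.
- Baselines low/high of 1-5/5-8 (M = 8), 1-8/10-15 (M = 15) and 1-15/20-60 (M = 60).
- 10% of low-flow and 30% of high-flow survivors ventilated from a random day between 2 and 11; other survivors recover linearly.

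About 3% to 6% of all death-survivor pairs were reversed. The gap below is the percentage of trials with nominal p < 0.05 when deaths share the worst rank, minus the percentage with the SAP score.

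| Mortality | Gap in percentage points |
|---|---|
| 30% v 5%, deaths three times likelier in high flow | 3.6 to 6.4 |
| 30% v 5%, no such concentration | 1.7 to 3.1 |
| 20% v 10% | 0.2 to 1.1 |

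With equal 15% mortality, both versions rejected in 4.2% to 5.3% of trials.

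**Mean difference.** Subtracting b at each day gives score = raw AUC - 13b. The unadjusted difference in mean scores is therefore the raw AUC difference minus 13 x the difference in mean baseline. An imbalance of 1 L/min contributes 13 L/min-days, with or without deaths. When baseline is a covariate, the treatment coefficient is the same for raw and baseline-subtracted AUC, so the planned ANCOVA is free of this term.

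**The case against.** The strongest reply is that the SAP contradicts nothing here. Section 7.2.1.1 describes an imputation, and the imputed flow is indeed the worst possible. The endpoint is a change from the patient's own baseline, and ranking that change is a legitimate choice. SAP Table 2 records the flow-scale death imputation as following an FDA recommendation. Section 7.2 leads with means, and the Wilcoxon test comes after them. No formal inference is planned, and nominal p-values are not to be read inferentially (SAP 5.3). Day-30 mortality and intubation-or-death at Days 14 and 30 have their own analyses (SAP 3.2.2, 7.3).

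Most of this stands, and it sets the size of the point. It does not change the arithmetic. Table 2 also shows an intention, stated for secondary endpoints 1, 2 and 5, to treat death as a highly unfavourable outcome, and the ranked score does not fully carry that through.

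A reader might infer that every rank-based analysis misplaces deaths. The documents do not support that. Section 7.2.1.4 does not say whether individual AUCs or daily values are ranked, or whether baseline is in the model. Table 3 extends the robustness analyses to the repeated-measures approach, which under 7.2.1.1 uses observed daily values, and a worst rank per patient has no defined meaning there. The point is therefore confined to the Wilcoxon test on individual AUC.

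**Conclusion.** The point holds in a limited form and is minor. That a death scores 13 x (M - b), and that reversals across different baselines are possible, follow from SAP 3.2.1 and 5.2 and need no assumption beyond the trapezoidal rule. How often reversals occur cannot be known from the documents. Under the assumptions shown, few pairs reverse, and the Wilcoxon result moves by about 2 to 6 points at 30% v 5% mortality and by about 1 point or less at 20% v 10%. The gap grows as deaths concentrate in high-baseline patients.

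Two stronger readings are tempting. One is that the plan generally scores death as a good outcome; at equal baseline it never does. The other is that the primary analysis is invalid or its error rate inflated; the primary presentation is descriptive, and with equal mortality the two versions behaved alike.

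Baseline imbalance in the mean is a separate matter. It is a chance effect that the planned ANCOVA already handles, so only the order of presentation is at issue.

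**What to change.** 1. In SAP 7.2, keep the planned Wilcoxon test and Hodges-Lehmann estimate on the SAP score. Beside them, add one labelled supportive Wilcoxon test on individual AUC, overall and in the 7.5 subgroups, in which all deaths through Day 14 share a tied worst rank. Give no Hodges-Lehmann estimate for that version, since its limits can depend on the arbitrary value assigned to death: in an illustrative 6 v 6 subgroup with one death, the upper limit was 79, 170 or 755 for death values of 104, 195 or 780. Do not apply the worst rank to the repeated-measures model.
2. Separately, present the ANCOVA of 7.2.1.2, with baseline oxygen and the stratification factors, as the lead estimate of the mean AUC difference, and show the unadjusted difference beside it.

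The cost is SAP wording and one recoded test, with no new data and no new model. The flow-scale death imputation stays as it is. The downside is that the added test is more sensitive to the number of deaths and has no matching effect estimate. If the data are already unblinded, report both beside the planned results as documented deviations in the CSR (SAP 1).

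As a separate small alignment, the timing of death in 3.2.1 (before Day 14) should be made to agree with 7.2.1.1 and Table 3, which count any death within the 14 days.

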#### **3.2.2** Secondary Efficacy Endpoints

The secondary efficacy endpoints are as follows:

1. Time to 50% reduction from baseline in supplemental oxygen based on oxygen flow in L/min

This endpoint will be based on the oxygen flow values used for the primary efficacy endpoint. It will be calculated as the number of days from baseline (Day 1) of study

Statistical Analysis Plan	RedHill Biopharma
Version: 3, Date: 13-DEC-2020	Study ABC-110

medication until the first day when the subject reached a value, which is at least 50% lower than the baseline value (the event of interest). Patients who early terminate the study before reaching this reduction will have their time censored at the last valid observation time point. Patients who will die within the followup timeframe will be censored at the time of the end of the follow-up period, thus taking the highly unfavorable possible outcome for this endpoint. The time frame for this endpoint is from Day 1 until end of off-study-drug followup. Additional analysis will be performed in the time frame of the 14-day-treatment DB Phase period (sensitivity analysis).

To note, in order to focus this endpoint on sustained success, it implies increase in supplemental oxygen negating initial success would be followed for re-achievement of success. Further note, a patient who reached success but did not have any further data supporting this success (i.e. discharged from hospital still requiring oxygen and no further data supporting success afterwards), may be subject to sensitivity analysis where regarded censored at last evaluable time.

2. The percentage of patients no longer receiving supplemental oxygen for at least 24 hours by Day 14

This endpoint will be defined per subject as a binary ("Success" / "Failure") variable with "Success" indicating that a subject no longer receiving supplemental oxygen for at least 24 hours by Day 14, and "Failure" otherwise. Patients who will die within 14-days will be regarded as "Failure", corresponding to the highly unfavorable possible outcome.

To note, in order to focus this endpoint on sustained success, it implies need in supplemental oxygen negating initial success would be followed for re-achievement of success.

3. The time to two consecutive negative swabs for SARS-CoV-2 by PCR, at least 24 hours apart

This time to event endpoint will be calculated as the number of days from baseline (Day 1) of study medication until the first occurrence of two consecutive negative swabs for SARS-CoV-2 by PCR, at least 24 hours apart (the event of interest). Patients who early terminate the study before reaching this event will have their time censored at the last valid observation time point. Patients who will die within the follow-up timeframe will be censored at the time of the end of the follow-up period, thus taking the highly unfavorable possible outcome for this endpoint. The time frame for this endpoint is from Day 1 until end of off-study-drug follow-up. Additional analysis will be performed in the time frame of the 14-day-treatment DB Phase period (sensitivity analysis).

4. The time to two consecutive negative swabs for SARS-CoV-2 by PCR, at least 24 hours apart, followed by continued negative swabs

This time to event endpoint will be defined similarly to the 3rd secondary efficacy endpoint, where the event of interest is the first occurrence of two consecutive negative swabs for SARS-CoV-2 by PCR, at least 24 hours apart, followed by continued negative swabs. The time frame for this endpoint is from Day 1 until end of off-study-drug follow-up.

Additional analysis will be performed in the time frame of the 14-day-treatment DB Phase period (sensitivity analysis).

5. The percentage of patients requiring intubation and mechanical ventilation

The percentage of patients requiring intubation and mechanical ventilation by **Day 30** will will be defined per subject as a binary ("Failure" / "Success") variable with "Failure" indicating that a subject had a reported requirement of intubation and mechanical ventilation any time before 30-days following first study dose, and "Success" otherwise. Death during this time frame will be regarded as "Failure" as well.

The percentage of patients requiring intubation and mechanical ventilation by **Day 14** will also be estimated in a similar way. Death before day 14 will be regarded as "Failure" as well.

6. The time to intubation and mechanical ventilation.

This time to event endpoint will be calculated as the number of days from baseline (Day 1 of study medication) until the earliest date of a reported requirement of intubation and mechanical ventilation, or death. Subjects who early terminate the study alive and without such requirement will have their time censored at the last valid observation time point. The time frame for this endpoint is from Day 1 until Day 30 from first dose. Additional analysis will be performed in the time frame of the 14-day-treatment DB Phase period (sensitivity analysis).

 The percentage of patients with at least one measurement of fever at baseline (defined as temperature >38.0 C[100.4 F]), who are afebrile (defined as temperature <37.2C [99 F]) at Day 14

This endpoint will be defined per subject as a binary ("Success" / "Failure") variable with "Success" indicating that a subject with fever at baseline is reported as afebrile on Day 14. "Failure" will be assigned otherwise.

This endpoint will be calculated only to the population of subject having fever at baseline. Additionally, to address objective # 3 (To evaluate the proportion of afebrile patients at Day 14), endpoint and analysis will be applied to the entire mITT analysis set.

8. Mortality due to any cause at Day 30.

This binary endpoint will be defined per subject as a binary ("Failure" / "Success") variable with "Failure" indicating that a subject had died within 30 days from first dose. "Success" will be assigned for patients known alive at day 30.

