#### **6 BACKGROUND INFORMATION**

#### 6.1 COVID-19 Disease

COVID-19 is a newly recognized disease caused by a coronavirus virus, SARS-CoV-2. A flu-like illness was first noted in December, 2019, in Wuhan, China and was subsequently attributed to a virus similar to the SARS coronavirus, which is now designated as SARS-CoV-2. While the clinical spectrum has not yet been well defined, early reports suggest that SAR-CoV-2 infection ranges from asymptomatic infection to pneumonia and Adult Respiratory Distress Syndrome (ARDS) with multiorgan failure, that may lead to death (Zhou, 2020). In the Zhou study, the median duration of viral shedding was 20 days, with an interquartile range of 17-24 days and a maximum of 37 days. Common symptoms reported in the Zhou study for 191 patients were fever (94%), cough (79%), sputum production and fatigue (each 23%) and myalgia (15%). Bilateral pulmonary infiltrates were noted in 75% of patients on chest X-ray. Patients over 65 years and those with significant comorbidities, such as diabetes, cardiac or pulmonary disease, appeared to be more susceptible for developing severe infection and had a relatively higher mortality rate compared to younger, otherwise healthy patients.

The incidence of symptomatic and severe infection, as a proportion of infected patients, is not yet known, as test availability, utilizing Polymerase Chan Reaction (PCR) performed on nasopharyngeal swabs or other body fluids, has been limited.

For most individuals testing positive, COVID-19 currently appears to be self-limiting. The major threat to this viral pandemic is spread through a nonimmune population, and to those most at risk of severe infection. SAR-CoV-2 is highly contagious, with spread by aerosol and surface contact (van Doremalen, 2020) and potential fecal spread (Chen, 2020). As this is a newly identified disease, first noted in December 2019, and as testing and interpretation of data are in a very early stage, no specific therapy has demonstrated antiviral efficacy.

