#### 9 ELIGIBILITY CRITERIA

#### 9.1 Inclusion Criteria

- 1) Adult male or female  $\ge 18$  to  $\le 80$  years of age
- 2) Proven COVID-19 infection per RT-PCR assay of a pharyngeal sample (nasopharyngeal or oropharyngeal) AND pneumonia defined as radiographic opacities on chest X-ray
- 3) The patient requires supplemental oxygen at baseline
- 4) The patient, guardian or legal representative has signed a written IRB-approved informed consent
- 5) Male participants with female partners of child-bearing potential agree to one of the following methods of contraception during the treatment period and for at least 1 month after the last dose of study drug:
  - Abstinence from penile-vaginal intercourse and agree to remain abstinent.
  - Male condom, with female partner using a highly effective contraceptive method. (For further details regarding highly effective contraceptive methods please see section 9.3.)

In addition male participants must refrain from donating sperm for the duration of the study and for 1 months after last dose of study drug.

Male participants with a pregnant or breastfeeding partner must agree to remain abstinent from penile-vaginal intercourse or use a male condom during each episode of penile penetration for at least 1 months after the last dose of study drug

Female participants:

A female participant is eligible to participate if she is:

- d) not pregnant
- e) not breastfeeding
- f) not a woman of child-bearing potential (as defined in Section 9.3)
- d) a WOCBP who agrees to use a highly effective method of contraception consistently and correctly during the treatment period and for at least 1 months after the last dose of study drug (please see further details on Section 9.3).

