## 12.1.2 Screening (Day -3 to Day 1)

Prior to the initiation of study-specific screening assessments the Investigator or designee must provide the patient(s) a complete explanation of the purpose and evaluations (procedures and assessments) of the study. Subsequently, the patient, or legal representative, must sign and receive a copy of an Informed Consent Form and authorization of use and disclosure of protected health information (PHI) that was approved by the institutional review board (IRB). Once informed consent has been obtained, the eligibility of the patient will be determined, and Screening assessments will be performed. Screening may be performed prior to Baseline (Day -7 to -1) or on the same day as Baseline (Day 1)

- Signed informed consent
- Eligibility determination
- Complete medical history (including onset of COVID-19 symptoms)
- Concomitant medication assessment
- Baseline review of systems
- Physical examination
- Vital signs (temperature, blood pressure, pulse rate, respiratory rate and oxygen saturation by pulse oximeter)
- Weight if the patient is ambulatory
- Oxygen requirement (L/min)
- 12-lead electrocardiogram
- Chest Xray
- Nasopharyngeal or pharyngeal swab for SARS-CoV-2-PRC
- Serum chemistry
- CRP, D-Dimer, LDH, ferritin, cardiac troponin
- CBC with differential
- Urinalysis
- Serum pregnancy test (for women of childbearing potential) within 3 days prior to treatment

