#### Table 1:Study Procedures and Assessments

 daily assessments whilst patient is hospitalized; vital signs = temperature, blood pressure, pulse rate, respiratory rate and oxygen saturation by pulse oximeter and recording of supplemental oxygen requirement as oxygen flow (L/min)  record weight if patient is ambulatory

 pharyngeal samples for SARS-CoV-2 PCR are collected daily, per standard of care. For patients having nasopharyngeal swabs, the same nostril must be used during the study

 for patients on concomitant hydroxychloroquine, the 12-lead ECG will be repeated after 3 hours (±30mins) of initial dose, on Day 2 and Day 4

 Chest X-ray, lab draws will be at the discretion of the Investigator depending on patient clinical condition

 CRP=C-reactive protein, LDH=lactate dehydrogenase

 women of childbearing potential; serum pregnancy test must be negative within 3 days prior to randomization.

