### 6.4 Covid-19 Disease Information

Disease information will be summarized by treatment group and overall using ITT, mITT and Safety populations. Summaries will be presented with descriptive statistics as specified in section 5.1 above

- Reason for hospitalization
- Time from onset of symptoms to Hospitalization (Days)
- Time from onset of symptoms to diagnosis (Days)
- Time from onset of symptoms to randomization (Days)
- Time from diagnosis to hospitalization (Days)
- Time from diagnosis to supplemental oxygen (Days)
- Time from diagnosis to randomization (Days)
- Time from hospitalization to supplemental oxygen (Days)

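### Both swab-clearance endpoints are analysed in the whole mITT without requiring a positive pre-dose swab, so patients already PCR-negative at entry can count as early clearance events and dilute the comparison

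*SAP*

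**What the plan says.** **Entry.** Inclusion criterion 2 (protocol 9.1, same in the synopsis) asks for "Proven COVID-19 infection per RT-PCR assay of a pharyngeal sample (nasopharyngeal or oropharyngeal) AND pneumonia defined as radiographic opacities on chest X-ray". It puts no limit on the age of the test or on time since onset. A swab is taken at screening (protocol 12.1.2: "Nasopharyngeal or pharyngeal swab for SARS-CoV-2-PRC") and again at Day 1 (Schedule of Assessments; SAP Table 1). No text makes either result a condition of entry or of analysis.

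**Endpoints.** Endpoint 3 is the number of days from Day 1 "until the first occurrence of two consecutive negative swabs for SARS-CoV-2 by PCR, at least 24 hours apart (the event of interest"). Endpoint 4 is the same with continued negativity afterwards. Neither asks for a preceding positive swab.

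**Analysis.** SAP 7.3 and Tables 14.2.4.1-2 and 14.2.5.1-2 use the mITT, which SAP 4.4 defines by randomization and one dose. The Cox model contains treatment and, if possible, the three stratification factors (age, HbA1c, oxygen type). It has no baseline-swab term. The only planned subgroup is oxygen type (SAP 5.6).

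**Contrast.** For endpoint 7 (fever), the SAP says "This endpoint will be calculated only to the population of subject having fever at baseline", and adds an analysis of the whole mITT beside it.

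**The concern.** A time-to-clearance endpoint describes patients who still carry detectable virus at time zero. Patients already negative cannot show a drug effect on clearance, yet the stated definition lets them supply events in the first days. Those events carry no treatment contrast but weigh heavily in a Cox model, because they occur when both risk sets are full.

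The protocol's rationale for opaganib is partly antiviral (section 6.3), and endpoints 3 and 4 are the only virological efficacy endpoints in the SAP. SAP 5.3 says results will be read through the overall pattern of benefit, so a blurred or unbalanced virological estimate feeds that reading directly, even without a formal test.

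**Working it through.** The plan states no effect size, event count or power for these endpoints, so there is no figure to reproduce. What follows checks how large the effect could be.

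**Step 1. How many could be negative at entry?** Protocol 6.1 reports, from a cited cohort, that "the median duration of viral shedding was 20 days, with an interquartile range of 17-24 days". I assume these durations run from symptom onset and follow a lognormal distribution:

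- sigma = ln(24/17) / (2 × 0.6745) = 0.3448 / 1.349 = 0.256
- share cleared by day d = Φ(ln(d/20) / 0.256)

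| Onset to Day 1 (assumed) | Share already cleared | Expected of 40 |
|---|---|---|
| 10 days | 0.3% | 0.1 |
| 14 days | 8% | 3 |
| 17 days | 26% | 10 |

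The interval is not in the documents. SAP 6.4 will tabulate it, but nothing caps it.

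**Step 2. Dilution of the hazard ratio.** Assumptions: true hazard ratio 2 among baseline-positive patients, exponential clearance, control median 12 days, 14-day time frame, and a share f negative at entry, all confirmed at once.

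- 14-day clearance among positives: control 1 − 0.5^(14/12) = 0.555; opaganib 1 − 0.5^(28/12) = 0.802
- Observed clearance per arm: f + (1 − f) × the value above
- Share of all events that are immediate: w = 2f / (sum of the two observed rates)
- Immediate events carry a log hazard ratio near 0, so the estimate is approximately exp[(1 − w) × ln 2]

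| f | Control | Opaganib | w | Approximate HR |
|---|---|---|---|---|
| 10% | 0.599 | 0.821 | 0.141 | 1.81 |
| 20% | 0.644 | 0.841 | 0.269 | 1.66 |
| 30% | 0.688 | 0.861 | 0.387 | 1.53 |

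Simulated Cox fits agree. Across set-ups differing in control median and in the handling of early events and ties, they gave 1.74 to 1.82 at 10%, 1.63 to 1.74 at 20% and 1.48 to 1.60 at 30%. With no drug effect the simulated hazard ratio stayed about 1 at every f.

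**Step 3. Absolute clearance.** At f = 20%, the rates rise from 55.5% and 80.2% to 64.4% and 84.1%. The difference shrinks from 24.7 to 19.8 percentage points, a factor of 1 − f.

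**Step 4. Partial confirmation.** An event needs a second negative. If only half of the 20% confirm and the rest behave like positives, about 10% are immediate, and Step 2 gives about 1.8. Simulation gave 1.79 to 1.85.

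**Step 5. Chance imbalance.** With 20 per arm and independent binomial counts, the probability that the arms differ by three or more baseline-negative patients is 18% at f = 10% and 36% at f = 25%. With no drug effect and a 5 versus 2 split, 14-day clearance is (5 + 15 × 0.555)/20 = 67% against (2 + 18 × 0.555)/20 = 60%.

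**The case against.** **One negative swab is not an event.** Correct, and it stands. Two are needed at least 24 hours apart, and endpoint 4 also needs continued negatives. SAP Table 1 says "pharyngeal samples for SARS-CoV-2 PCR are collected daily, per standard of care", but SAP 8.12 and protocol 12.1.4 say every 1 to 3 days, so the second swab may come later or be positive. Step 2 is therefore close to a worst case for a given f.

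**The assumed inputs pull against each other.** By the protocol's shedding figures, 10% to 30% negative means Day 1 about 14 to 17.5 days after onset. Remaining shedding among positives would then have a median of roughly 5 to 6 days, not 12. This is fair, although a wide spread of onset times would ease it. With a 5.5-day median, the Step 2 formula gives 1.85, 1.72 and 1.60: slightly less dilution, same direction. If patients enter around day 10, almost none are negative and the point has no practical weight.

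**The consequence is limited.** This also stands. SAP 5.3 treats nominal p-values as non-inferential, and Listings 16.2.10 and 16.2.12 would let a reader find these patients among 40.

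**The fever comparison.** Endpoint 7 is not only a restricted analysis. The SAP runs it in the whole mITT too, and the restriction comes from the protocol's own endpoint definition. It is a model for having both analyses, not evidence that the whole-mITT version is illegitimate.

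**Stronger readings that do not hold.** A reader might infer that the rule favours opaganib. It does not: allocation is randomized, and the early events arise in both arms. A reader might also infer from the diagnosis-to-randomization summary in SAP 6.4 that late enrolment is expected. That is a descriptive table and says nothing about expected intervals.

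**Conclusion.** The gap in the text is clear: no baseline-swab condition, covariate or handling rule exists for endpoints 3 and 4, and eligibility does not close it. Its size is uncertain because the share negative at entry is unknown. Under an assumed true hazard ratio of 2, with 10% to 30% negative and all confirmed, the estimate falls to roughly 1.8 to 1.5. It falls less if confirmation is incomplete, and negligibly if enrolment is early in the illness. The expected distortion is dilution, raised clearance rates and chance imbalance at 20 per arm. What is affected is the interpretation of two secondary endpoints, not a planned decision. This is a worthwhile, inexpensive improvement rather than a flaw that undermines the trial.

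**What to change.** In SAP 3.2.2 and 7.3:

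1. Analyse endpoints 3 and 4 in mITT patients whose last available swab before the first dose was positive, using the baseline definition in SAP 5.2.
2. State how a missing pre-dose swab is handled, for example by retaining the patient on the strength of the qualifying positive PCR.
3. Report by arm how many patients were negative at baseline and how many had no pre-dose swab.
4. Keep the whole-mITT analysis alongside as a sensitivity analysis.
5. Say whether the Day 1 swab can be the first of the pair, and whether the event is dated at the first or second negative. The SAP settles neither.

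**Cost.** SAP wording only, since the swabs are already scheduled. The analysis set for two secondary endpoints becomes somewhat smaller. If only about half of baseline-negatives would have confirmed, restriction brings no gain in precision, only a cleaner question. Selection rests on one pre-dose swab that may be falsely negative. A Day 1 swab is also pre-dose but not necessarily pre-randomization, so the restricted set should not be described as free of all bias; blinding and the parallel mITT analysis limit that risk.
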